Official Title: Intraoperative Monitoring and Management Protocol to Reduce Strokes
(IMMPRES): Pilot Study

NCT04543838

Document Date: 6/23/2022

Study Protocol

If the patient is eligible, interested, and provides consent, they will complete initial preoperative baseline surveys and assessments. These assessments include: Medical History, Medications, Neurological Exam, NIH stroke Scale, Questionnaire for Verifying Stroke-Free Status (QVSFS), Delirium Screen, Modified Rankin Scale, Barthel Index, Digit Symbol Substitution Test (Cognitive Assessment), Trail Making Test part B (TMT-B) (Cognitive Assessment), and Montreal Cognitive Assessment (MoCA) (Cognitive Assessment), Depression Scale, and Quality of Life scale. General history, risk factor profile and physical examination (H&P) will be performed prior to entering the study. Neurological examinations, NIHSS, Modified Rankin Scale and Barthel Index will be performed by study neurologist. A Questionnaire for Verifying Stroke-Free Status (revised Questionnaire for Verifying Stroke-Free Status (QVSFS)), QOL assessment, Delirium and Cognitive assessment will be administered to each potentially eligible patient by a research coordinator. Subjects of child bearing age will complete a pregnancy test.

Baseline surveys and assessment will be collected during a pre-operative session, either in conjunction with a pre-op clinic visit in-person prior to surgery during their surgical admission. This will allow maximum flexibility in timing, without interfering with clinical care.

Clinically collected data will be abstracted from the electronic medical record (EMR) for research purposes. We will review the patients preoperative medical records to screen patients for the use of intraoperative monitoring. This is currently a standard clinical practice. After enrollment, the subject will be randomized into the control or intervention group. Subjects will be computer randomized to condition 1:1. It will take approximately a half an hour to complete surveys and study procedures. On the day of surgery, EEG and somatosensory evoked potentials assessments will be performed preoperatively. The study team will code data to distinguish remote from in person assessment on the individual instruments.

Procedure: The cardiac surgeons who will be performing surgery will be informed by the principal investigator. The medical management of patients before, during, and after the procedure will be continued as routine medical care in standard medical therapy group. In the intervention group, standard medical therapy with intraoperative monitoring and management protocol will be done. Our IMMP will be a) intraoperative monitoring with SSEP and EEG during surgery and continued for 4 hours after; b) management protocol will be treating patients based on a SSEP and/or EEG changes. In patients with bilateral SSEP and/or EEG changes, we will aim for a MAP target of the greater of 20% above the patient's preoperative baseline or an absolute threshold of 80 mmHg. In patients with persistent unilateral SSEP and/or EEG changes, the higher MAP target will be maintained followed by immediate post-operative evaluation for stroke.

In the control group, the patient will receive standard of care.

Post-Procedure/Pre-Discharge: Brief history and physical examination daily while patient is in hospital. Neurological examination performed by study Neurologist. Delirium screen will be performed. NIH Stroke Scale (NIHSS) performed by study neurologist 18 to 54 hours post procedure. MRI will be performed before discharge. The MRI will be completed at the MRI Research Center. This trial will include 1.5 T MRI scanners. All subjects will have continuous monitoring with a pulse-oximeter. MR technologists will monitor pulse-oximeter. They will terminate the scan, and call an investigator to evaluate the subject, if pulse-oximeter data goes below/above some defined threshold (sustained heart rate over 100 bpm, oxygen saturation below 90%). The responsible investigator for each study scan when scheduled and who will be available to respond if necessary will be selected on a case-by-case basis in REDCap "MRI Completion" instruments. The Digit Symbol Substitution Test (Cognitive Assessment), Trail Making Test part B (TMT-B) (Cognitive Assessment), and Montreal Cognitive Assessment (MoCA) (Cognitive Assessment) will be performed.

Follow-up: At 30 days post-op: Modified Rankin Scale, Barthel Index, Questionnaire for Verifying Stroke-Free Status (QVSFS), Quality of Life Assessment, Digit Symbol Substitution Test (Cognitive Assessment), Trail Making Test part B (TMT-B) (Cognitive Assessment), and Montreal Cognitive Assessment (MoCA) (Cognitive Assessment) will be performed. The Cognitive Assessments (DSST, TMT-B, & MoCA) & Neurological Assessments (MRS & The Barthel Index) through mail and telemedicine/Microsoft Teams.

Follow-up: At 3 months: Neurological exam, Modified Rankin Scale, Barthel Index, TIA/Stroke Questionnaire, Quality of Life Assessment, Digit Symbol Substitution Test (Cognitive Assessment), Trail Making Test part B (TMT-B) (Cognitive Assessment), and Montreal Cognitive Assessment (MoCA) (Cognitive Assessment) will be performed. The Cognitive Assessments (DSST, TMT-B, & MoCA) & Neurological Assessments (MRS & The Barthel Index) through mail and telemedicine/Microsoft Teams.

Follow-up: At 1 year: Neurological exam, Modified Rankin Scale, Barthel Index, TIA/Stroke Questionnaire, Quality of Life Assessment, Digit Symbol Substitution Test (Cognitive Assessment), Trail Making Test part B (TMT-B) (Cognitive Assessment), and Montreal Cognitive Assessment (MoCA) (Cognitive Assessment) will be performed. The Cognitive Assessments (DSST, TMT-B, & MoCA) & Neurological Assessments (MRS & The Barthel Index) through mail and telemedicine/Microsoft Teams.

Assessments and Questionnaires:

1. NIH Stroke Scale (NIHSS): The NIHSS was specifically designed for assessment of interventions in clinical trials. Rather than measuring function specifically, the NIHSS operates a 15-item ordinal, non-linear, neurological impairment scale covering consciousness, ocular movement, vision, coordination, speech and language, sensory function, upper and lower limb strength, facial muscle function, and hemi-neglect⁶¹. NIHSS became the gold standard for stroke severity rating after the first successful trial in acute stroke therapy⁶².
2. Stroke/TIA Questionnaire: The Questionnaire for Verifying Stroke-Free Status

(QVSFS) 50 is an 8-item structured interview designed to identify stroke-free individuals. The QVSFS has negative predictive value of the QVSFS was 0.96, with positive predictive value of 0.71. The QVSFS can effectively identify stroke-free individuals with a high degree of accuracy, even in a population with a large proportion of patients with prior stroke or TIA.

3. Cognitive Assessment: The Montreal Cognitive Assessment (MoCA), a widely used test will be used measure to assess cognitive decline. It has shown to be superior to the Mini-Mental State Exam (MMSE) in evaluation of executive, visuo-spatial and language skills after stroke^{63,64}. The MoCA instrument assesses multiple cognitive domains⁶⁵: visuospatial abilities, executive functions, short-term memory recall, attention, concentration, working memory, language, and orientation to time and space and we feel this will provide a thorough assessment of the impact of acute perioperative covert stroke. MoCA scores range from 0 to 30 with higher a higher score indicating superior cognitive function. A decrease of 2 points or more in MoCA score is perceived to be important to patients, and has been used as a cut-off for important cognitive decline.^{21,66} The Digit Symbol Substitution Test (DSST) is a widely used sensitive test to evaluate cognitive decline across a wide range of clinical populations. DSST evaluates cognitive speed, attention, and executive functions by requiring participants to match symbols to numbers within a 120 second time limit using a key.⁶⁷ Scores range from 0 to a maximum of 133 with a higher score indicating superior cognitive ability. We will utilize a decrease of 5 or more points on the DSST is considered clinically meaningful cognitive decline on the basis of differences in score observed between patients aged 70 and 75 years old in the Cardiovascular Health Study^{68,69}. The Trail Making Test part B (TMT-B) is the widely used test for cognitive decline after cardiac procedures.⁵⁶ The TMT-B measures cognitive domains of processing speed, sequencing and mental flexibility by measuring the time (in seconds) to connect numbers and letters

randomly placed on a page in an alphanumerical order, alternating between numbers and letters. Completion times between 78 and 128 seconds are considered average for adults aged 75 to 98 years of age. We will use a threshold of an increase of 10% or more in TMT-B completion time has been considered meaningful cognitive decline in a recent sub study of the HOPE-3 trail.

4. Modified Ranking Scale(mRS). The Modified Rankin Scale (MRS) is a brief physical function assessment, which covers the entire range of functional outcomes from no symptoms to death, has demonstrated validity with measures of stroke pathology (eg, infarct volumes) and agreement with other stroke scales. It is widely used in clinical trials⁷² and has demarcated effective and ineffective acute stroke therapies in trials with appropriately powered sample sizes⁷³.

5. Barthel's index: The BI operates according to a 10-item scale in which patients are judged upon degree of assistance required when carrying out a range of basic activities of daily living (ADL). The assessment is a validated questionnaire comprising a total score of 100 for the 10 items of the scale. The patient's answers on each item are scored based upon actual ability (preferably observed by the assessor). The usual scoring for each item is 0 points for "no ability" to do the item independently, 5 points for "moderate help" with the item, and 10 points for being able to manage the item independently. The BI has emerged as the second most popular tool for assessment of

post-stroke outcome in clinical stroke trials74.

6. Delirium Assessment: We will utilize modified Confusion Assessment Method (CAM)52, 3D CAM59 for hospitalized patients and ICU CAM75 for patients in the ICU to evaluate for delirium. 3D CAM, a 3-minute structured assessment has a sensitivity of 95% [84%, 99%] and specificity of 94% [90%, 97%] to identify delirium in the hospital76. In a large systematic review, ICU CAM to diagnose delirium had a pooled sensitivity of the CAM-ICU was 80.0% (95% confidence interval (CI): 77.1 to 82.6%), and pooled specificity of 95.9% (95% CI: 94.8 to 96.8%). Delirium after cardiac surgery can be high (41%) and an Independent Predictor of Functional Decline.

7. Quality of Life assessments: We will utilize EuroQol 5-dimension (EQ-5D) questionnaire to assess the patients' health-related quality of life. EQ-5D is a self reported questionnaire designed to measure the health status and can be collection by phone or video interview. The EQ-5D questionnaire consists of two parts. The first part contains the EQ-5D descriptive system, comprising of 5 questions regarding mobility, selfcare, usual activities, pain, and depression (scores range from 0 to 1). The second part is a vertical, visual analogue scale with the end-points of "best imaginable health state" and "worst imaginable health state" (scores range from 0 to 100). EQ-5D has been used as a measure of health-related quality of life in patients who have suffered an clinical stroke7879, covert stroke21, and in those undergoing cardiac surgery.

8. Assessment of Depression: Depression after stroke affects approximately one third of stroke survivors in the first year after stroke, with a cumulative incidence of 55%.81,82 We will use the 9 – item Patient Health Questionnaire to measure the incidence of depression. The 9-item Patient Health Questionnaire (PHQ-9) (sensitivity: 0.86; 95% CI, 0.70–0.94; specificity: 0.79; 95% CI, 0.60– 0.90) appeared to be the optimal measures for screening and was suggested to be more pragmatic 83.

Intraoperative Neurophysiological Monitoring: Blood

pressure management will be institutional standard of care as determined by the Anesthesiologist per standard of care. Electroencephalography (EEG): EEG recording and analysis during carotid surgery has as previously described by the group18. Electrode placement on the scalp is based on the international 10-20 EEG system. EEG recording will start after anesthesia had been successfully induced and continue throughout the procedure. We will record 16 channel EEG system The EEG recording parameters are as follows: notch filter 60 Hz, the band pass filter for 1-70 Hz; sensitivity will vary between 5-7 microvolts/div and a time base of 30 mm/sec. Significant EEG changes, will be defined as a loss of in the amplitude of fast frequency and /or increase of delta activity by more than two fold15. A raw digital and quantitative EEG will be processed using software provided by the Natus Medical ® Pleasanton, CA.

Somatosensory evoked potentials (SSEP): SSEP recording and analysis during cardiac surgery will be performed as previously described by the group18. We will independently stimulate the bilateral median nerve at the wrist using adhesive sticky pad electrodes. Scalp electrodes will be placed at P4/Fz and P3/Fz will be placed per the international 10–20 system. A cervical electrode is localized at the CV2, and peripheral electrodes are placed at the erb's point bilaterally (EPs and EPd). Three channels of data will be collected for each median nerve SSEP: FZ-P4/P3 to record the cortical potential, FZ-CV2 to record the cervical potential, and EPs-EPd to record the

erb's point potential. Stimulation frequency will be set to 2.33-2.41 Hz with duration of 0.2-0.3 milliseconds. Band pass filters are set at 10-300 Hz for the cortical channel, 30-1,000 Hz for the cervical channel, and 100Hz- 1 kHz for the erb's point channel. The analysis time is 100 milliseconds. Significant SSEP changes, a variable of interest will be defined as greater than 50% decrease in the amplitude N20-P30 in SSEP in the Fz-P4/P3 channel 14any time during.

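### The PHQ-9 is meant to measure incidence of depression, but a depression scale is scheduled only before surgery

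*Protocol*

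**What the plan says.** In the Protocol, Assessments and Questionnaires, item 8 chooses the 9-item "Patient Health Questionnaire to measure the incidence of depression". The reason given is longitudinal: "Depression after stroke affects approximately one third of stroke survivors in the first year after stroke, with a cumulative incidence of 55" per cent. Item 8 states no time point for the questionnaire.

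The timing therefore has to come from the visit lists:

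- **Baseline** (opening section of the Study Protocol) includes a depression scale: "Montreal Cognitive Assessment (MoCA) (Cognitive Assessment), Depression Scale, and Quality of Life scale".
- **Post-Procedure/Pre-Discharge** has the neurological examination, "Delirium screen will be performed. NIH Stroke Scale (NIHSS) performed by study neurologist 18 to 54 hours post procedure", then MRI and the three cognitive tests. No depression scale is named.
- **30 days**: "At 30 days post-op: Modified Rankin Scale, Barthel Index, Questionnaire for Verifying Stroke-Free Status (QVSFS), Quality of Life Assessment", then the three cognitive tests.
- **3 months**: "At 3 months: Neurological exam, Modified Rankin Scale, Barthel Index, TIA/Stroke Questionnaire, Quality of Life Assessment", then the three cognitive tests.
- **1 year**: "At 1 year: Neurological exam, Modified Rankin Scale, Barthel Index, TIA/Stroke Questionnaire, Quality of Life Assessment", then the three cognitive tests.

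No depression scale appears in any of the three follow-up lists. The SAP's Statistical Analysis section does not mention depression.

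**The concern.** Incidence counts new cases arising over time among people free of the condition at the start. It cannot be obtained from one assessment made before the exposure of interest, which here is surgery and any perioperative stroke. As scheduled, the PHQ-9 supplies one preoperative score per patient and nothing afterwards. Item 8 therefore states a purpose that the visit schedule cannot meet.

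This is a data-collection gap, so a later analysis decision cannot repair it. A site that follows the lists will hold no postoperative PHQ-9 scores. The trial could then neither report new depression on this instrument nor describe it by arm. As a pilot for a larger trial, it would also yield no information on postoperative PHQ-9 scores or completion rates.

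**Working it through.** The plan gives no figure to reproduce, and no sample size or power formula applies. The check compares the visit lists with the purpose stated in item 8.

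**Step 1. Identify the instrument.** The baseline list names a depression scale without naming the PHQ-9. Item 8 describes the PHQ-9, and no other depression instrument is described anywhere. I take the two to be the same.

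**Step 2. Count how often each baseline scale recurs.** The baseline list contains ten scales, leaving aside history, medications and the neurological examination. Each is looked up in the four postoperative lists.

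| Baseline scale | Pre-discharge | 30 days | 3 months | 1 year | Times listed |
|---|---|---|---|---|---|
| NIHSS | yes | – | – | – | 1 |
| Delirium screen | yes | – | – | – | 1 |
| QVSFS | – | yes | yes* | yes* | 3 |
| Modified Rankin | – | yes | yes | yes | 3 |
| Barthel | – | yes | yes | yes | 3 |
| Quality of life (EQ-5D) | – | yes | yes | yes | 3 |
| DSST | yes | yes | yes | yes | 4 |
| TMT-B | yes | yes | yes | yes | 4 |
| MoCA | yes | yes | yes | yes | 4 |
| Depression scale | – | – | – | – | 0 |

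*Listed as the TIA/Stroke Questionnaire, which item 2 identifies with the QVSFS.

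Nine of ten scales recur at least once. The depression scale is the only one that does not, at 0 of 4 points.

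**Step 3. Ask whether inclusion could be implied.** The lists are itemised and name the other instruments again at each visit, so silence on one of them cannot be read as inclusion. The opening section also says who administers the other nine scales (the study neurologist or a research coordinator) but names no assessor for the depression scale. Its operational details look unfinished.

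**Step 4. Ask what can be estimated.** Incidence = new cases after baseline ÷ patients free of depression at baseline. The baseline score can supply the denominator. With no later administration, the numerator is never observed. What remains is the proportion screening positive before surgery.

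**The case against.** Several points can fairly be made on the other side.

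- **Depression is covered at follow-up by the EQ-5D**, described in item 7 as "comprising of 5 questions regarding mobility, selfcare, usual activities, pain, and depression". That is one question among five. Item 8 names the PHQ-9 and supports it with the PHQ-9's own sensitivity and specificity, and nothing designates the EQ-5D question as the depression measure. This does not answer the concern.
- **Incidence may be used loosely for the frequency of positive screens.** This is possible, since item 8 also calls the PHQ-9 a screening tool. The repair would then be a small change of wording. But the rationale in item 8 concerns the first year after stroke, which does not fit a measure taken only before surgery.
- **The issue is minor, and no comparison of depression between arms is promised.** Both parts stand. The available text ranks depression nowhere as an outcome, and item 8 promises only to measure incidence. The sample size rests on covert stroke with a composite primary outcome. No stated analysis is biased and no power figure changes.
- **Part of the SAP was not available for this check**, so depression may have a role that cannot be seen. This limits what can be said about its rank as an outcome. It does not alter the mismatch, which lies wholly within the Protocol.
- **A single screen does not give the prevalence of depression.** This is correct. With the quoted sensitivity of 0.86 and specificity of 0.79, it gives the prevalence of positive screens, and the wording here follows that.

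**Conclusion.** The concern holds. Item 8 and the visit lists contradict each other: the stated purpose needs at least one postoperative PHQ-9, and 0 of 4 postoperative lists contain a depression scale, against 9 of 10 baseline scales that recur. The documents do not show whether follow-up PHQ-9 was left out by mistake or never intended, and the mismatch needs correcting in either case.

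The conclusion rests on one assumption, that the baseline depression scale is the PHQ-9. If another scale were meant, the PHQ-9 would be scheduled nowhere and the conflict would be worse. The consequence is confined to an ancillary measure as far as the available text shows. It is worth correcting because uncollected scores are lost for good and the correction is cheap.

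**What to change.** Decide which of the two texts reflects the intention, and make the other agree.

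**If follow-up is intended:**

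1. Add the PHQ-9 to the 30-day, 3-month and 1-year lists, at the same contact as the EQ-5D, and name it in the baseline list.
2. State the screening cut-off in advance. Item 8 quotes sensitivity and specificity without the cut-off they belong to, whereas item 3 gives decline thresholds for MoCA, DSST and TMT-B.
3. Count incident cases among patients below the cut-off at baseline, and call the result screen-positive incidence. The label matters. At specificity 0.79, 1 − 0.79 = 0.21, so about 21% of such patients who never become depressed would screen positive at a given follow-up if screening errors were independent between visits. The quoted interval of 0.60 to 0.90 gives 40% to 10%. Perfectly correlated errors would bring the figure to 0%. Both error patterns are assumptions, since the documents give no information on them.
4. If arms are to be compared, compare the follow-up score with adjustment for the baseline PHQ-9.

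The cost is a short amendment and 9 items × 3 contacts = 27 items per patient over one year, at contacts that already take place.

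**If follow-up is not intended,** or those contacts have already passed, delete the incidence statement and describe the PHQ-9 as a baseline measure only. The cost is one sentence.

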**Statistical Analysis:**

This study will attempt to improve over previous work (summarized in meta-analysis: [J Am Heart Assoc. 2019 May 7;8(9): e010920]), which predominantly used overt and covert strokes as (binary) outcome measures. Drawing from the reported incidence of covert stroke of 33% and anticipating a reduction to 11% in the intervention group, we calculate a power of 78% with 40 subjects per group (alpha = 0.05, calculations in SamplePower, ver 3, SPSS/IBM). The use of a composite primary outcome serves to bolster the power calculation and proposed pilot sample size.

However, we expect to need far fewer patients to show a significant effect in the tertiary outcome related to DWI lesions, for two important reasons. First, a great deal of previous work has been done at low MRI field strength, predominantly 1.5 T. We will utilize 3 T field and modern 32/64 channel head coils with multiband imaging sequences, which will improve DWI resolution and signal to noise ratio. Second, we will count the number of DWI lesions and measure their total volume in the MRI images, providing a more granular (continuous) measure to compare between study groups. As DWI lesions are a known mediator of clinically symptomatic strokes, even showing a small but statistically significant change in number or extent of DWI lesions should provide proof of concept that the IMMPRES intervention is worth further exploration in a fully-powered (externally funded) clinical trial

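### The stated 78% power matches a one-sided 0.05 test; read as two-sided, the same inputs give about 67–69%

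*SAP*

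**What the plan says.** The sample-size paragraph of the SAP (Statistical Analysis) sets the rates: "Drawing from the reported incidence of covert stroke of 33% and anticipating a reduction to 11% in the intervention group". From these it states: "we calculate a power of 78% with 40 subjects per group (alpha = 0.05, calculations in SamplePower, ver 3, SPSS/IBM". The next sentence adds: "The use of a composite primary outcome serves to bolster the power calculation and proposed pilot sample size". The Protocol (Study Protocol) gives the allocation: "Subjects will be computer randomized to condition 1:1".

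The text available for review does not say which test the 78% refers to, whether alpha is one- or two-sided, or whether a continuity correction was used. It also gives no event rates for the composite. One part of the SAP was not available for review, so these statements are limited to the text that was.

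**The concern.** The calculation has four numerical inputs (two rates, a group size and alpha) and one output, so it can be checked directly. A reader who enters them with the usual two-sided 0.05 does not get 78%.

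This is the only power figure in the available text, and it supports the group size of 40. Two things turn on which reading is right:

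- **Two-sided 0.05.** The trial is more likely to miss its planned effect than the plan says, and a null result for covert stroke would be weaker evidence against the intervention.
- **One-sided 0.05.** The power is as stated, but the nominal chance of falsely declaring benefit is twice that of a two-sided 0.05 test (5% against 2.5%).

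The available text does not let the reader tell which applies.

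**Working it through.** **Inputs.** Control rate p1 = 0.33, intervention rate p2 = 0.11, n = 40 per group and alpha = 0.05 (SAP, Statistical Analysis); 1:1 allocation (Protocol, Study Protocol). The difference is d = 0.33 − 0.11 = 0.22 and the average rate is 0.22.

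**Standard errors.**
- Pooled: SE0 = √(2 × 0.22 × 0.78 / 40) = 0.09263
- Unpooled: SE1 = √((0.33 × 0.67 + 0.11 × 0.89) / 40) = 0.08930

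**Reproducing the SAP's figure.** With the pooled z-test, power = Φ((d − z × SE0) / SE1).
- One-sided 0.05, z = 1.645: Φ((0.22 − 0.1524) / 0.0893) = Φ(0.757) = 77.6%, which rounds to the stated 78%.
- Two-sided 0.05, z = 1.960: Φ((0.22 − 0.1816) / 0.0893) = Φ(0.431) = 66.7%.

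**Other methods, same inputs.** The unpooled z-test uses Φ(d / SE1 − z), with d / SE1 = 2.464. The arcsine method uses Φ(h√(n/2) − z), with h = 2 arcsin√0.33 − 2 arcsin√0.11 = 0.5477 and h√20 = 2.450. The chi-square, Fisher and Yates rows sum the binomial probabilities of all outcome pairs that the test rejects.

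| Method | Two-sided 0.05 | One-sided 0.05 |
|---|---|---|
| Pooled z | 66.7% | 77.6% |
| Unpooled z | 69.3% | 79.4% |
| Arcsine | 68.8% | 79.0% |
| Uncorrected chi-square, enumerated | 68.5% | 79.1% |
| Fisher's exact | 59.3% | 71.1% |
| Yates-corrected chi-square | 56.2% | 68.9% |

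Further variants fit the same pattern. Two-sided, the mid-p test gives 62.1%, the log odds ratio 62.5% and the log risk ratio 58.9%. No two-sided 0.05 method tried exceeds 69.3% at the stated rates. Not every uncorrected one-sided method reaches 78% (log odds ratio 73.7%, log risk ratio 70.5%), but every method within two points of 78% is one-sided and uncorrected.

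**Could rounding of the rates explain it?** The range below covers the first four methods in the table, two-sided 0.05.
- Exact 1/3 vs 1/9: 67.2–69.9%
- Most favourable rounding, 33.5% vs 10.5%: 70.7–73.4%
- Least favourable rounding, 32.5% vs 11.5%: 62.5–64.9%

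None reaches 78%. Unequal allocation is ruled out by the 1:1 randomisation.

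**Size of the gap.** The two-sided miss rate is 100 − 69.3 = 30.7% to 100 − 66.7 = 33.3%, against 100 − 78 = 22% as stated. For scale only, 78% power at two-sided 0.05 is first reached at 50 per group (unpooled z, arcsine, chi-square enumeration) to 52 per group (pooled z).

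**Does the composite close the gap?** The available text gives no composite rates, so this step rests on an assumption: added events are independent of covert stroke and occur in a proportion q of controls, with q from 0.02 to 0.41. The composite rates are then 1 − 0.67(1 − q) in controls and 1 − 0.89(1 − q × RR) in the intervention group, where RR is the risk ratio for the added events. By two-sided pooled z, against 66.7% for covert stroke alone:
- RR = 1/3, the ratio implied by 11% / 33%: power rises to 68% at q = 0.02 and 94% at q = 0.41.
- RR = 1, no effect on the added events: power falls to 63% at q = 0.02 and 21% at q = 0.41.

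A composite can therefore raise or lower power, depending on how strongly treatment affects the added events.

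**The case against.** The strongest reply is that nothing was miscalculated. A one-sided pooled test gives 77.6%, which rounds to the stated figure, and neither document says two-sided. This stands in part: the 78% is a correct one-sided result, and the fault is that it is presented without the condition that makes it correct. The shortfall depends on the usual reading of an unqualified alpha.

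The test or its sidedness may be given in the part of the SAP that was not available. That limits the claim of omission but not the arithmetic. If that part says one-sided, the condition belongs beside the figure. If it says two-sided, the 78% is wrong.

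The 67–69% range holds for the common uncorrected tests only. That is correct: a planned Fisher or Yates test would have lower power, 59.3% or 56.2% two-sided, so the restated figure must match the test actually planned.

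The composite calculation rests on assumed rates and on independence, which may well not hold. It shows only that the direction is uncertain, and the main conclusion does not need it.

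Finally, this is a pilot that looks ahead to a larger trial and does not claim full power. That lowers the stakes and is a reason not to ask for more patients. It does not excuse a power figure, offered in support of the sample size, that cannot be interpreted as written.

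**Conclusion.** The concern holds and should be fixed. With 33% vs 11%, 40 per group and 1:1 allocation, 78% is the power of an undeclared one-sided 0.05 test without continuity correction. Under a two-sided 0.05 uncorrected test, power is about 67–69%, roughly ten points lower. Confidence in the arithmetic is high, because it uses only the plan's own inputs and the gap exceeds anything that rounding or choice of standard test can produce. Which reading the sponsor intended, and which settings were used in the software, cannot be established from the available text.

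**What to change.** Choose one of two wordings for the sample-size paragraph.

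1. **Two-sided.** State that with 40 patients per group the power to detect 33% vs 11% is about 68% (two-sided alpha 0.05, uncorrected chi-square test). If another test is planned, name it and give its own power.
2. **One-sided.** Keep 78%, state beside it that the test is one-sided at 0.05 and which test is used, justify that choice, and apply the same test in the analysis.

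On the composite: if its expected rates appear elsewhere in the plan, cite them next to the sentence that relies on it, with the power they give. If they do not, do not use that sentence as support for the 78%.

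The cost is SAP wording only. The first option makes the stated power less favourable; the second requires a justification. Neither needs added enrolment.

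### The only power figure in the text provided is for covert stroke alone and matches a one-sided test; no calculation shows that the composite primary outcome adds power

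*SAP*

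**What the plan says.** The SAP, under Statistical Analysis, takes its event rates from one outcome: "Drawing from the reported incidence of covert stroke of 33% and anticipating a reduction to 11% in the intervention group". On those rates the result is "we calculate a power of 78% with 40 subjects per group", with the settings given as "alpha = 0.05, calculations in SamplePower, ver 3, SPSS/IBM". Whether the test is one- or two-sided is not stated. The next sentence moves to a different outcome: "The use of a composite primary outcome serves to bolster the power calculation and proposed pilot sample size". No event rate, treatment effect or power for that composite accompanies it.

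The Protocol gives equal allocation ("Subjects will be computer randomized to condition 1:1"). Under Post-Procedure/Pre-Discharge it schedules an MRI before discharge and allows a scan to be stopped on pulse-oximeter readings. It gives no expected rate of stopped or missing scans.

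**The concern.** The power figure and the primary outcome do not match. The figure describes covert stroke, and the composite is then offered as extra support without a number. More events do not by themselves mean more power. A component that the monitoring and management protocol does not change adds events to both arms. It either narrows the difference between them or leaves the difference unchanged with more variance around it.

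The SAP uses the composite to support the proposed pilot sample size. A reader may therefore take 78% as a floor for the primary comparison. If it is not, a null result on the composite would be read as coming from a better-powered comparison than the trial actually made. The unstated sidedness adds to this, because it moves even the covert-stroke figure by about 11 points.

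**Working it through.** **Inputs.** From the SAP, Statistical Analysis: p1 = 0.33, p2 = 0.11, n = 40 per group, alpha = 0.05, stated power 78%. From the Protocol: 1:1 allocation. Component rates, effects, overlap and numbers lost below are assumptions.

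**Step 1: reproduce the stated figure.** Pooled-variance normal approximation:

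power = Φ{ [ |p1 − p2| − z·√(2p̄(1 − p̄)/n) ] / √([p1(1 − p1) + p2(1 − p2)]/n) }

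- p̄ = (0.33 + 0.11)/2 = 0.22
- √(2 × 0.22 × 0.78/40) = 0.0926
- √((0.2211 + 0.0979)/40) = 0.0893
- One-sided, z = 1.645: (0.22 − 0.1524)/0.0893 = 0.757, power **77.6%**
- Two-sided, z = 1.960: (0.22 − 0.1815)/0.0893 = 0.431, power **66.7%**

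Other methods give, two-sided: unpooled 69.3%, arcsine 68.8%, exact-enumerated chi-square 68.5%, Fisher exact 59.3%, continuity-corrected 56.0%. One-sided: unpooled 79.4%, arcsine 79.0%, Fisher exact 71.1%, continuity-corrected 68.3%. No two-sided variant tried reaches 78%. With the pooled formula, 80% power two-sided needs 55 per group.

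**Step 2: add one binary component** with control rate q and relative risk r, and count a patient with either event as a composite event.

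- Independent of covert stroke: control 1 − 0.67(1 − q); intervention 1 − 0.89(1 − qr)
- Non-overlapping: control 0.33 + q; intervention 0.11 + qr

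For q = 10% and 40 per group:

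| Component effect | Overlap | Control vs intervention | Two-sided | One-sided |
|---|---|---|---|---|
| Covert stroke alone | – | 33.0% vs 11.0% | 67% | 78% |
| r = 1 (unaffected) | independent | 39.7% vs 19.9% | 49% | 62% |
| r = 1 (unaffected) | non-overlapping | 43.0% vs 21.0% | 56% | 68% |
| r = 0.8 | independent | 39.7% vs 18.1% | 57% | 69% |
| r = 0.5 | independent | 39.7% vs 15.5% | 69% | 79% |
| r = 1/3 | independent | 39.7% vs 14.0% | 75% | 84% |
| r = 1/3 | non-overlapping | 43.0% vs 14.3% | 82% | 90% |

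With an unaffected independent component, the difference shrinks from 22.0 to 19.8 points. With an unaffected non-overlapping one, it stays at 22 points but the variance rises. If the added event occurs only in patients already counted for covert stroke, power does not change.

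**Step 3: break-even.** This is the r at which composite power equals that for covert stroke alone. It is the same one- or two-sided.

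| q | Independent | Non-overlapping |
|---|---|---|
| 5% | 0.54 | 0.72 |
| 10% | 0.55 | 0.75 |
| 20% | 0.58 | 0.80 |
| 41% | 0.63 | 0.90 |

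Below the break-even the composite gains power; above it the composite loses power. The SAP's own relative risk for covert stroke is 0.11/0.33 = 0.33.

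**Step 4: fewer evaluable patients**, covert stroke alone. At 36 per group, 62% two-sided and 74% one-sided. At 32 per group, 57% and 69%.

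**The case against.** The strongest reply is that composites are used to gain power and that this one may do so. That stands as a possibility. A component can respond less than covert stroke and still help: at a 10% rate and relative risk 0.5, two-sided power rises from 67% to 69%. A reader might infer that every added component must fall about as much as covert stroke. The break-even values show that this is too strict.

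A reader might also infer that even a fully responsive composite falls short, because 75% two-sided is below the stated 78%. That compares different bases. Like for like, the same component raises power from 67% to 75% two-sided, or from 78% to 84% one-sided.

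SAP text that may define the composite was not available for this review. Its definition cannot be called missing, and composite rates given there cannot be excluded. A binary any-event composite is itself an assumption.

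The Protocol says "Delirium after cardiac surgery can be high (41%) and an Independent Predictor of Functional Decline", and it is tempting to enter that rate as an unaffected component, which gives 21% two-sided if independent. Nothing in the text provided makes delirium part of the primary outcome, and the non-overlapping case at the same rate gives 53%. The 41% serves here only as the upper end of an assumed range.

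Finally, this is a pilot. That limits the weight of the point but does not remove it, since the SAP itself uses power to support the pilot's size. The scan-stopping rule implies that some outcomes may be lost, but not how many.

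**Conclusion.** The point holds as a gap in justification. In the text provided, the only power figure describes covert stroke, and the statement that the composite strengthens it has no calculation behind it. The figure itself is a one-sided result: 77.6% one-sided against about 67% two-sided, a gap of about 11 points if the planned test is two-sided. That the trial intends a one-sided test is a possible inference, but the SAP does not say so.

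The direction of the composite's effect on power is open. For a 10% independent component, power runs from 49% to 75% two-sided, or 62% to 84% one-sided, as the relative risk goes from 1 to one third. A reader might conclude that the composite lowers power. The documents do not support that either; they leave the matter undetermined. These ranges assume one added binary component, the stated overlap patterns and all 40 per group evaluable.

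**What to change.** 1. State whether alpha of 0.05 is one- or two-sided, and restate the covert-stroke power to match (about 67% if two-sided).
2. Delete the sentence on the composite. Alternatively, replace it with power for the composite from its own expected control and intervention rates, with the assumed component effects and overlap written out.
3. Show power for fewer evaluable patients as a sensitivity figure, for example at 36 and 32 per group, labelled as assumed losses.

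Keep the sample size. The cost is one recalculation and a few lines of SAP text. The downside is a less favourable stated power if the test is two-sided or the added components respond weakly.
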